7 SAFETY MANAGEMENT

7.1 Clinical Adverse Events

Clinical adverse events (AEs) will be monitored throughout the study.

7.2 Adverse Event Reporting

Since the study procedures are not greater than minimal risk, SAEs are not expected. If any unanticipated problems related to the research involving risks to subjects or others happen during the course of this study (including SAEs) they will be reported to the IRB in accordance with CHOP IRB SOP 408: Unanticipated Problems Involving Risks to Subjects. AEs that are not serious but that are notable and could involve risks to subjects will be summarized in narrative or other format and submitted to the IRB at the time of continuing review.

If a participant becomes more symptomatic (based on parent/child report or clinical judgment), without resolution for at least four weeks, the study treatment provider will review the participant's clinical status with the project team and PI. Concerns about deterioration will trigger an evaluation conducted by school's behavioral health staff and then discussion with the PI regarding whether discontinuation from the study is in the best interests of the child. Such participants will be removed from the study and treated openly with appropriate clinical care.

In cases where concern about danger to self or others is identified, the behavioral health staff – with consultation with CHOP consultants, as needed – will conduct further assessment of the child's mental status and decide on a course of action. If the assessment leads to the conclusion that the child is at risk for suicide, the behavioral health staff will work with the family to take the child to the emergency room for evaluation and treatment. If the child returns to school after visiting the emergency room and it is determined that an outpatient, school-based level of care is appropriate, he or she may continue to participate in study interventions. If it is determined that a higher level of care is appropriate, the child will be withdrawn from the study and will receive the higher level of care.

If previously undocumented sexual or physical abuse is discovered during eligibility assessment, behavioral health staff at the schools will implement standard procedures for notifying the State social welfare authorities (per state law and standard procedure in the respective school district), and defer further evaluation if needed until the child has been released from agency review. If state involvement is identified or mandated at any point during the study, the child may or may not be continued in treatment depending on what is in the best interests of the child. This decision will be made by the PI and treating counselor at the site in coordination with the child's legal guardians and state/local authorities. If the child returns to school after receiving emergency services, he or she will continue to participate in interventions in the school setting.

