4.4 Subject Completion/Withdrawal

Subjects may withdraw from the study at any time without prejudice to their care, education or employment. They may also be discontinued from the study at the discretion of the Investigator for lack of adherence to the study and/or development of exclusionary criteria. Student participants will be removed from the study if they develop exclusionary criteria during the trial or if it is determined that the intervention group is not age/developmentally appropriate based on the grade level of the majority of enrolled students. It will be documented whether or not each subject completes the clinical study. If the Investigator becomes aware of any serious, related adverse events after the subject completes or withdraws from the study, they will be recorded in the study files.

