6.3 Statistical Methods

Data will be analyzed using an intent-to-treat approach, wherein each participant (BHS or student) will be kept in the arm to which the school was randomized, regardless of treatment

received. In addition to creating pre/post change scores and analyzing the data using t-tests (or the Wilcoxon signed rank test), a mixed-effects model will be explored for analyzing the pre/post repeated-measures endpoints related to student academic engagement and mental health symptoms. A student-level random effect will be included and modeled using the unstructured covariance matrix to account for within-subject dependence due to repeated measurements. The models will include study arm (RTS or CC) and time of measurement (pre/post) as fixed effect. Arm x Time interaction effects will be included in the model as well. This modeling approach will allow us to compare pre-to-post changes and the extent to which these changes differ across study arms. For the purpose of generating statistical estimates for an anticipated phase 3 larger scale study, the nested nature of students within the school as well as BHS within the school will be explored using a hierarchical mixed effect multilevel model. Furthermore, we will explore marginal models using generalized estimating equations (GEE; ^{74,75}), which will produce robust estimates that adjust for clustering at the school level. Although SAS PROC MIXED will not remove participants with post-missing data from the analysis, missing data will be kept to a minimum. As a sensitivity analysis, we will impute the potential missing data using the maximum likelihood method for imputation. ⁷⁶

For the mixed-methods analyses (survey and semi-structured interview data about perceived appropriateness, feasibility, and acceptability of the training and consultation procedures, and BHS's opinions about the support they received), we will use the same data analytical approach described in IRB Protocol # 20-017895.

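### Students removed for worsening may leave no post-treatment score, and the planned sensitivity analysis cannot test for the bias this could cause

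*Combined protocol and SAP*

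**What the plan says.** **Who leaves the study.**
- Section 7.2: unresolved worsening over at least four weeks leads to a review, an evaluation by school staff and a "discussion with the PI regarding whether discontinuation from the study is in the best interests of the child". The next sentence is "Such participants will be removed from the study and treated openly with appropriate clinical care".
- Section 7.2, for a child who needs more than school-based care: "the child will be withdrawn from the study and will receive the higher level of care".
- Section 8.4.2 (risks of group interventions): the investigator withdraws a child who shows unusually high distress.
- Section 4.4: "Student participants will be removed from the study if they develop exclusionary criteria during the trial". A second ground there is a group judged unsuitable for the student's age or development, going by the grade of most of its members. Discontinuation is also possible, at the investigator's discretion, for "lack of adherence to the study".

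**What happens to their data.** Section 6.3 sets an intent-to-treat approach in which "each participant (BHS or student) will be kept in the arm to which the school was randomized". Section 3.2 has students take part for as long as their intervention lasts. Section 5.4 schedules student outcomes at two points only, before and after treatment. No section says whether post-treatment measures are taken from a student who has been removed.

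**How missing scores are handled.** Section 6.3 plans change-score t-tests (or a Wilcoxon test), an exploratory mixed model that retains students without a post score, and exploratory multilevel and GEE models. It has one sensitivity analysis for missing data: "we will impute the potential missing data using the maximum likelihood method for imputation". Section 6.4 assumes uniform attrition of 15% and counts 268 evaluable students out of 312.

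**The concern.** Keeping a student in the randomised arm protects the comparison only if there is an outcome to analyse. Removal for lasting worsening, high distress or need for higher care happens between the two measurement points, so what triggered it enters none of the models. The missing post score may then depend on the outcome that was not observed. A likelihood-based mixed model handles loss that depends on observed data. It does not handle this kind, and filling in values by maximum likelihood rests on the same assumption.

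The changes in BASC-3 scales and academic engagement are primary student endpoints (section 6.1). The pilot exists to estimate effect sizes (section 6.4) and to supply estimates for a larger trial (section 6.3). Selective loss of the worst outcomes would carry into that trial's planning.

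**Working it through.** **Inputs.** From section 6.4: 104 students per arm (312 in total), 15% attrition, 89 per arm analysed, SD of change 8, half-width 2.4. Removal rates by arm or reason are not in the documents, so every rate below is an assumption. So are the pre/post correlations.

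**1. The plan's own figures.**
- 312 × 0.85 = 265.2. Per arm, 104 × 0.85 = 88.4, rounded up to 89, and 3 × 89 = 267. The stated 268 agrees to rounding.
- Half-width = t(0.975, 176) × 8 × √(2/89) = 2.37, stated as 2.4. This reproduces.

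**2. What each analysis does with a removed student who has no post score.**
- Change-score test: no change can be formed, so the student is dropped.
- Mixed model: the baseline value stays in the randomised arm. The missing post value is in effect predicted from baseline, using students of that arm who stayed.
- Maximum-likelihood imputation: the same prediction under the same assumption.

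**3. Complete-case bias.** Count a positive change as worsening. If the worst fraction q of a normal distribution with SD 8 is removed, the arm's mean change looks better by 8 × φ(z₁₋q)/(1 − q):
- q = 3%: 0.56
- q = 5%: 0.87
- q = 10%: 1.56
- q = 15%: 2.19

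With no true effect, the false arm difference is the difference between two shifts. For 10% versus 3% it is 1.56 − 0.56 = 1.00 point. For equal rates it is zero, although each arm's own mean change is still shifted.

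**4. The same under maximum likelihood.** In a large simulation with change SD 8 and pre/post correlation 0.3 to 0.7, post was regressed on pre among students who stayed, then predicted at the full-arm baseline mean.

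| Removed (arm A vs arm B) | Complete cases | Maximum likelihood |
|---|---|---|
| 5% vs 5% | 0 | about 0 |
| 5% vs 10% | 0.69 | 0.51 to 0.62 |
| 5% vs 15% | 1.33 | 1.03 to 1.22 |

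Maximum likelihood leaves between 0.51/0.69 = 74% and 1.22/1.33 = 92% of the bias. If the same proportions held for 10% versus 3%, the 1.00 point would become about 0.7 to 0.9.

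**5. One common rule in both arms, with a real effect.** Suppose every student who worsens by more than a fixed amount (8 to 12 points, correlation 0.5) is removed, and the true difference is −4. Fewer students cross the line in the better arm: 6.7% versus 15.9% at 8 points, and 2.3% versus 6.7% at 12 points. The estimate shrinks to between −2.81 and −3.32 in complete cases, and to between −2.98 and −3.44 under maximum likelihood. Unequal detection is therefore not needed for bias, and here the bias is towards no effect.

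If post scores were still collected from all removed students and analysed by randomised arm, the true value would be recovered in every one of these scenarios.

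**The case against.** Several points on the other side stand.

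- **Intent-to-treat.** A reader might infer that the removal rules contradict section 6.3 outright. They do not. Sections 4.4 and 7.2 govern study participation, section 6.3 governs the arm in which a student is analysed, and no section excludes removed students from analysis. Loss of their post scores is inferred from silence, together with section 3.2 ending participation with the intervention.
- **Automatic removal.** A reader might also infer that every student who worsens is removed. Section 7.2 puts an evaluation and a discussion first, and lets a child return after an emergency visit if school-based care is judged suitable. Section 8.4.2 answers deterioration during treatment with referral. The quoted sentence of 7.2 nevertheless reads as unconditional, so these passages need to be reconciled. This review takes no view on the clinical rule.
- **Other reasons.** Poor fit is judged on grade level, and the exclusionary conditions in section 3.3.2 are not worsening on the study scales. These removals need not bias anything. The argument rests on worsening, distress and higher-care removals.
- **Differences between arms.** Coaching in RV+ does discuss student behaviour (section 4.3.1), so detection could differ. But section 5.3 has all group sessions recorded and coded and CI/CO records reviewed monthly, without limiting either to RV+, and the trigger in 7.2 is the same in all arms. Differential detection is possible but not shown.
- **Sensitivity analysis.** It would go too far to say that it must agree with the main result by construction. Section 6.3 also plans change-score tests and GEE, which can differ from a likelihood fit. The narrower point survives: agreement between two missing-at-random analyses is not evidence about loss that is not at random.
- **Size.** The truncation figures require those removed to be the worst on the scale analysed. With seven student scales, the same children need not be worst on each.

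**Conclusion.** The point holds as a gap in the plan. Students can leave the study for reasons tied to a poor course, no section secures their post-treatment scores, and no planned analysis examines departures from missing at random. Intent-to-treat is weakened in practice rather than broken in the text.

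The size cannot be established from the documents. The illustrative 1.0 point, about two fifths of the stated 2.4 margin, rests on three assumptions: 10% versus 3% removed, those removed being the worst changers, and SD 8. Lower or more equal removal, or removal only loosely tied to the scale analysed, gives less. Direction is also open. Heavier removal in one arm flatters that arm, while a common rule with a real effect shrinks the estimate. The documents support neither a claim of known bias nor a claim that RV+ is favoured.

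**What to change.** This is a cheap improvement that leaves the clinical removal rules as they are.

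1. In sections 4.4, 7.2 and 8.4.2, separate stopping the intervention from stopping data collection. Amend section 3.2 so that participation for data purposes does not end with the intervention.
2. Seek the existing parent, teacher and student post-treatment measures for every enrolled student unless consent for data is withdrawn, and analyse them in the randomised arm. Define the time, for example when the student's school or group completes post-treatment assessment. This is needed because section 5.4 gives no date and CI/CO runs for a variable period (section 1.2.4).
3. Record the reason for each removal and report removals by arm.
4. Alongside or in place of the maximum-likelihood analysis, add one missing-not-at-random sensitivity analysis, such as delta-adjusted imputation by arm that respects school clustering. Section 6 says the SAP is still to be finalised before database lock, so there is room for it.

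**Cost.** A wording change to protocol and consent, modest programming, and a few extra questionnaires. At the section 8.7 rates, $20 to the parent and $20 to the teacher make at most $40 per removed student. Some families will decline, so the sensitivity analysis is needed even with continued collection.

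### Section 7.2 contradicts itself on whether a child continues in the interventions after emergency care, and does not say which situations its closing sentence covers

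*Combined protocol and SAP*

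**What the plan says.** Section 7.2 deals with continuation after a serious event in two consecutive paragraphs that have different triggers.

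- **Suicide-risk paragraph.** It opens with concern that a child may harm himself, herself or someone else. Behavioral health staff, with the sponsor's consultants if needed, assess the child and choose what to do. The emergency room step follows "If the assessment leads to the conclusion that the child is at risk for suicide". On return there are two branches. The first has a double condition, "If the child returns to school after visiting the emergency room and it is determined that an outpatient, school-based level of care is appropriate", and its consequence is permissive: "he or she may continue to participate in study interventions". The second is "If it is determined that a higher level of care is appropriate, the child will be withdrawn from the study".

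- **Abuse and state-involvement paragraph.** It starts from abuse discovered at the eligibility assessment and then widens: "If state involvement is identified or mandated at any point during the study". For such a case the rule leaves both outcomes open: "the child may or may not be continued in treatment depending on what is in the best interests of the child". The principal investigator and the treating counselor make that decision, together with the guardians and the authorities. The paragraph closes with: "If the child returns to school after receiving emergency services, he or she will continue to participate in interventions in the school setting".

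Section 8.4.2 refers readers to Section 7.2 as a whole, not to one paragraph of it, for what to do about suicidal ideation.

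**The concern.** The closing sentence of the abuse paragraph changes both the condition and the force of the rule. Just before it, continuation is a judgment made by named roles and can go either way. In the closing sentence, continuation follows from return to school alone.

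Its scope is also unclear. It refers to emergency services, but nothing earlier in its paragraph sends a child to any. The only emergency care described elsewhere in Section 7.2 is the emergency room visit in the suicide-risk paragraph, so a reader looking for the antecedent is led back to that pathway, where a different rule applies.

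These are among the most serious events the protocol foresees, and staff in 24 schools would be acting on the text. Two schools could follow different sentences of the same section and act differently for children in the same position. The rule also decides which students are withdrawn, so it should be applied in the same way in all three arms.

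**Working it through.** No arithmetic applies: the point uses no sample size, effect size or error rate, and the plan gives no figure to reproduce. The check is a comparison of the three continuation rules.

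| Rule | Trigger | Condition for continuing | Force | Who decides |
|---|---|---|---|---|
| Suicide-risk paragraph | Suicide risk, emergency room visit | Return to school and a finding that school-based care is suitable | *May* continue; withdrawn if higher care is suitable | Behavioral health staff assess and choose the action; the level-of-care finding itself is in the passive voice |
| Abuse paragraph, best-interests rule | State involvement | Judgment of the child's interests | May or may not continue | Principal investigator and treating counselor, with guardians and authorities |
| Abuse paragraph, closing sentence | Emergency services, source not stated | Return to school only | *Will* continue | Nobody named |

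Applying these rules to the possible cases:

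1. *State involvement, no emergency care.* Only the best-interests rule applies. No conflict.
2. *State involvement, emergency care, return to school, decision in favour of continuing.* Both sentences lead to continuation. No difference in outcome.
3. *State involvement, emergency care, return to school, decision against continuing.* The best-interests rule stops treatment and the closing sentence continues it. This contradiction needs no assumption about scope beyond the closing sentence applying to the paragraph in which it stands.
4. *Suicide risk, emergency room visit, return to school, school-based care found suitable.* One rule permits continuation and the other, if general, requires it. The outcome differs only if the discretion is used not to continue.
5. *Suicide risk, return to school, level of care not yet determined.* The suicide-risk paragraph's condition is not met. The closing sentence, if general, is satisfied.
6. *Suicide risk, return to school, higher level of care found suitable.* The suicide-risk paragraph withdraws the child. The closing sentence, if general, continues the child.

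Case 3 is therefore a contradiction inside one paragraph. Cases 4 to 6 are conflicts between paragraphs, and they arise only if the closing sentence is read as general or if one child meets both triggers.

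**The case against.** The strongest reply is that the two paragraphs answer different questions. One governs suicide risk and the other abuse and state involvement, and a sentence at the end of a paragraph is normally read within it. A sympathetic reader would add that the closing sentence merely describes what happens once the best-interests decision has favoured continuing. The first part stands: the clash with the suicide-risk paragraph is conditional on scope. The second part would remove case 3, but the sentence contains no such condition.

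Three stronger readings are tempting, and the documents do not support them.

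- *A child judged to need higher care would be kept in the interventions.* A reader might infer this from the closing sentence taken alone and as general. The suicide-risk paragraph expressly withdraws that child, and the closing sentence mentions neither suicide nor level of care.
- *Nobody is assigned to decide in suicide-risk cases.* The level-of-care finding is worded in the passive, but the same paragraph gives behavioral health staff the assessment and the choice of action. What is missing is an explicit link from that role to the finding made on return.
- *A child would re-enter without any review.* Section 8.4.1 makes the principal investigator responsible for the safety of the interventions, with weekly team meetings and immediate reporting of adverse events to the IRB. Section 8.4.2 adds on-call support from a licensed psychologist, covering suicidal ideation and abuse, and withdrawal by the principal investigator for unusually high distress. These provisions do not amend the sentence, but they make unreviewed re-entry less likely.

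**Conclusion.** The point holds as a contradiction of wording with an undefined scope. Within the abuse paragraph, a discretionary rule is followed by an automatic one. If the closing sentence is general, it also departs from the suicide-risk paragraph in both condition and force. The first conflict rests only on the closing sentence applying to its own paragraph. The second depends on the general reading, which the text neither states nor excludes.

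The size cannot be given as a number. A reader might apply an assumed rate of emergency visits to the 312 planned students, but the documents give no such rate. The result would also count too many children, because in case 2, and in case 4 whenever the discretion is used to continue, the outcome is the same under either sentence. Nor can any effect on precision or error rates be derived.

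The correction is still worth making: followed literally, a stated safety rule overrides the plan's own case-by-case decision, and the repair is small.

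**What to change.** Amend Section 7.2 so that:

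- the closing sentence of the abuse paragraph is reconciled with the best-interests rule before it and with the suicide-risk paragraph;
- it states which situations it covers, including what emergency services refers to;
- the role that makes the decision on return is named where the text leaves this open, that is, for the level-of-care finding in the suicide-risk paragraph and for the closing sentence itself.

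Whether continuation is automatic or conditional, and whether the suicide-risk and abuse pathways should share one rule, are clinical decisions for the investigators and the IRB. This review takes no position on them.

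The change is one or two sentences, with no cost in staff, data or sample size.
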